6.3. General Concomitant Medication and Supportive Care Guidelines

Antiemetics

The prophylactic use of a 5-HT3-antagonist is strongly recommended before the TMZ administration. Additional standard antiemetics are permitted as required.

CYP450 Interactions

Neither ABT-888 nor TMZ are known to have significant cytochrome P450 interactions. However, because there is a potential for interaction of ABT-888 or TMZ with other concomitantly administered drugs, the case report form must capture the concurrent use of all other drugs, over-the-counter medications, or alternative therapies.

Hematopoietic growth factors

Use of colony stimulating factors (GCSF) is permitted at the discretion of the treating physician if they believe it to be in the subject's best interest. Because the population of subjects eligible in this study may have significant prior therapy, it is possible that the study treatment may result in leucopenia. Standard erythropoiesis stimulating agents may be used at the treating physician's discretion. Transfusions of RBC are permitted at physician discretion.

Bisphosphonates

Use of standard bisphosphonates such as zoledronic acid is permitted.

Anticancer therapy

Concomitant medications (hormonal therapy, chemotherapy, biologic therapy, targeted therapy) intended to treat the underlying cancer are not permitted.

Glucocorticoid steroids

Use of steroids for the treatment of progressive brain metastases will be considered evidence of clinical progression.

Other medications

Investigators may prescribe other concomitant medications or treatments deemed necessary to provide adequate supportive care except as noted in Section 6.3.

6.4. Duration of Therapy

Duration of therapy will depend on individual response, evidence of disease progression and tolerance. In the absence of treatment delays due to adverse events, treatment may continue indefinitely or until one of the following criteria applies:

- Disease progression (note: see Section 6.6 for CNS-only progression),
- Intercurrent illness that prevents further administration of treatment,
- Unacceptable adverse event(s),
- Participant decides to withdraw from the study,
- General or specific changes in the participant's condition render the participant unacceptable for further treatment in the opinion of the treating investigator, or
- Study drug becomes unavailable due to manufacturer or other causes.

6.5. Duration of Follow Up

Participants will be followed for two years after removal from study. . Participants removed from study for unacceptable adverse events will be followed until resolution or stabilization of the adverse event. Patients will be followed off study by their primary treating physician. At the time of informed consent, patients will be asked for permission to contact the patient or their family in the future after coming off therapy to determine patient outcome or if any relevant follow up issues arise from the clinical or exploratory endpoints.

6.6. Criteria for Removal from Study

Participants will be removed from study when any of the criteria listed in Section 6.4 applies. The reason for study removal and the date the participant was removed must be documented in the study-specific case report form (CRF). Alternative care options will be discussed with the participant.

In the event of unusual or life-threatening complications, participating investigators must immediately notify the Principal Investigator [name] at [contact].

NOTE: Participants without evidence of progression of visceral disease who develop CNS progression (isolated new brain metastases or progression of brain metastases) treatable with radiation as their only site of progression may be allowed to continue to receive protocol based therapy. Such participants may continue on protocol therapy until either they experience systemic progression of their non-CNS disease and/or further progression in the brain (by investigator assessment). Such participants are advised not to initiate radiation within 14 days of last dose of study drug (unless clinical care requires more urgent initiation of radiation), and the next cycle of study drug should not resume until \geq 7 days after radiation is complete. A delay of up to 9 weeks is permitted to allow for radiation therapy. Participants must have ECOG performance status ≤ 2 when resuming study drug, and restaging CT scans

(chest/abd/pelvis) should be obtained \leq 4 weeks of restarting study drug and will serve as the new baseline to assess non-CNS response.

7. EXPECTED TOXICITIES AND DOSING DELAYS/DOSE MODIFICATIONS

Dose delays and modifications will be made using the following recommendations. Toxicity assessments will be done using NCI Common Terminology Criteria for Adverse Events (CTCAE v3.0) which is available at <http://ctep.cancer.gov/reporting//ctc.html>.

If possible, symptoms should be managed symptomatically. In the case of toxicity, appropriate medical treatment should be used (including anti-emetics, anti-diarrheals, etc.).

All adverse events experienced by participants will be collected from the time of the first dose of study treatment, through the study and until the final study visit. Participants continuing to experience toxicity at the off study visit may be contacted for additional assessments until the toxicity has resolved or is deemed irreversible.

Dose may be delayed as described in Section 7.2.

A list of the adverse events and potential risks associated with the agents administered in this study appear below and will determine whether dose delays and modifications will be made or whether the event requires expedited reporting **in addition** to routine reporting.

7.1. Anticipated Toxicities

7.1.1. ABT-888

Preliminary safety data are available for 24 subjects from Study M06-862, a dose ranging phase 1 study of ABT 888 and TMZ.²⁶ Twenty-two of the 24 subjects (91.7%) experienced at least 1 adverse event. The most common adverse events, reported in $> 30\%$ of the subjects, were nausea (66.7%), fatigue (58.3%), thrombocytopenia and vomiting (54.2% each), anorexia (45.8%), neutropenia (37.5%), and constipation (33.3%). Among adverse events considered possibly or probably related to ABT-888, the most common were nausea (58.3%); fatigue (54.2%); thrombocytopenia (50.0%); and neutropenia, vomiting, and anorexia (37.5% each). Additional adverse events reported by at least 2 subjects and considered possibly or probably related to ABT-888 included anemia, leukopenia, abdominal pain, constipation, diarrhea, pyrexia, dizziness, headache, alopecia, petechiae, and rash; in addition, clinically significant events of febrile neutropenia and stomatitis also were seen in 1 patient each.²⁶

Eight of 24 subjects (33.3%) experienced a serious adverse event in Study M06-862. The most commonly reported serious adverse event was vomiting (3 subjects, 12.5%). Additional serious adverse events considered possibly or probably related to ABT-888 were neutropenia and nausea (2 subjects each, 8.3%), and febrile neutropenia, leukopenia, thrombocytopenia, gastrointestinal hemorrhage, hematemesis, pyrexia, pneumonia, and dehydration (1 subject each, 4.2%). No dose relationship has been established for these events.²⁶

No subject has died during Study M06-862, and no pregnancies have been reported.

As with any medication, allergic reactions are a possibility. Problems and side effects may occur with the use of ABT-888 that are not expected or are unknown at this time.

7.1.2. Temozolomide

Known potential toxicities of TMZ are hematological toxicities (leucopenia, lymphopenia, thrombocytopenia, and anemia), renal insufficiency, nausea and vomiting, liver enzyme abnormalities, lethargy, rash, headache, alopecia, constipation, fatigue/malaise, anorexia, hyperglycemia and diarrhea are known toxicities. Refer to the package insert³⁰ (<http://www.spfiles.com/pitemodar.pdf>) for additional information on adverse events observed to date. Rats given TMZ in recent multidose toxicity studies have developed adenocarcinoma of the breast, fibrosarcomas, malignant Schwannomas (a variant of fibrosarcoma), keratoacanthomas and basal cell adenomas. Similar studies conducted in dogs did not reveal any similar findings. The significance of this finding for humans is not known presently. The expected toxicities of the combination of TMZ and ABT-888 are described above in Section 7.1.1.

7.2. Dose Modifications/Delays

Blood counts will be evaluated within -3 days prior to day 1 of each cycle. Subject must have an ANC \geq 1500/ μ l and platelet count \geq 100,000/ μ l within -3 days of day 1 of each cycle. On day 1 of each cycle (within -3 days) all clinically significant treatment related **non-hematological** toxicity grade 3 or 4 (except for alopecia) must have resolved (CTCAE grade \leq 1 or baseline). If toxicity persists, treatment should be delayed for up to 3 consecutive weeks. If after 3 weeks of delay all clinically significant treatment related toxicity has still not resolved then any further treatment with TMZ and ABT-888 should be stopped (subject is off treatment). Study drug interruptions for events that are clearly not related to the study drug, e.g., underlying cancer, planned surgical procedures or acute viral illnesses, should not necessitate a dose reduction and treatment may be delayed as necessary beyond 3 weeks.

Dose reductions:

ABT-888 Dose Reduction and Delay

The following are guidelines for dose reduction, delay and discontinuation of ABT-888.

- ABT-888 dose reduction and delay guidelines are summarized in Table 7.2.1.
- ABT-888 should be discontinued at the same time of discontinuation of TMZ.
- For any subject who experiences Grade 3/4 toxicity which is not attributable to TMZ or the underlying disease, the ABT-888 dose will be discontinued until the toxicity resolves to Grade 1 or lower or to baseline if Grade 2 at the time of study entry. The dose of ABT-888 will be reduced to a dose of 20 mg every 12 hours. Only one ABT-888 dose reduction is allowed. If a subject experiences a second Grade 3/4 toxicity which is not attributable to TMZ or the underlying disease and is thought (by the treating physician with consultation of the principal investigator as needed) to be related to the ABT-888, subject must discontinue study treatment.

- Any event of seizure, regardless of grade or attribution, requires interruption of ABT-888 and discussion with the Principal Investigator regarding the decision to resume treatment, and the Abbott Oncology Safety Desk (Section 12.5.1) should be notified.

Temozolomide Dose Reduction and Delays

Clinically significant hematological toxicities should result in TMZ dose reduction or delay. During treatment, CBCs should be monitored and the next cycle of therapy should not be started unless the ANC is $> 1500/\mu\text{L}$ and platelet count is $> 100,000/\mu\text{L}$. For any Grade 3/4 toxicities attributable to TMZ, dose reduction and/or delay guidelines should be followed per Table 7.2.1. Dose reductions in the next cycle should be based on lowest blood counts and worst non-hematologic toxicity observed in the previous cycle. The $75 \text{ mg/m}^2/\text{day}$ dose is the lowest dose of TMZ that is allowed in this study. Subjects must stop TMZ and ABT-888 if they are at the $75 \text{ mg/m}^2/\text{day}$ dose level of TMZ and require an additional dose reduction (per Table 7.2.1) due to toxicities. Temozolomide dose levels to be used for dose reductions are summarized in Table 7.2.2.

For TMZ dosage calculations based on body surface area please refer to Appendix B.

Important:

- If the dose was **reduced or delayed** for toxicity, there will **be no dose re-escalation**.
- Any event of seizure that was clearly attributable to ABT-888 requires discontinuation of ABT-888.

Table 7.2.1 ABT-888 and TMZ Dose Reduction or Delay

	Adverse Event	Dose Reduction
Hematologic Toxicity attributable to TMZ	ANC < 1000/ μ L* and/or Platelets < 50,000/ μ L*	
 1. Hold TMZ and ABT-888. Check CBC weekly until recovery to: ANC > 1500/μL and platelets > 100,000/μL and 2. Reduce TMZ dose by 1 dose level at the next cycle***
	ANC 1000/ μ L* to 1500/ μ L* Platelets 50,000/ μ L* to 100,000/ μ L*	
 1. Hold TMZ and ABT-888. Check CBC weekly until recovery to ANC > 1500/μL and platelets > 100,000/μL and 2. Maintain Current TMZ Dose at the next cycle
Non-hematologic Toxicity attributable to TMZ	Nausea/Vomiting CTC \geq Grade 3 despite optimal antiemetic therapy	
 1. Delay cycle until Grade 1 (or Grade 2 if present at baseline) and 2. Reduce TMZ dose by 1 dose level for the next cycle***
	Fatigue, constipation, anorexia or headaches CTC \geq Grade 3	
	Any other CTC \geq Grade 3 deemed to be clinically significant by PI	
	Adverse Event	Dose Reduction**
Attributable to ABT-888	Any Grade 3 or 4 toxicity which is not attributable to TMZ or underlying disease	
 1. Delay cycle until Grade 1 (or Grade 2 if present at baseline) and 2. Reduce ABT-888 dose to 20 mg q12 hrs . and 3. Reduce TMZ dose by 1 dose level for the next cycle

* Regardless of attribution.

** There will only be one ABT-888 dose reduction allowed.

*** TMZ dose cannot be reduced below 75 mg/ m^2 /day.

Table 7.2.2 Temozolomide Dose Level Definition Summary

Dose Level	Temozolomide Dose
1	200 mg/ m^2 /day
2	150 mg/ m^2 /day
3	100 mg/ m^2 /day
4	75 mg/ m^2 /day

[figure not shown]

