6.2.2. Temozolomide

Dosing

TMZ will be administered orally once a day for 5 consecutive days on days 1-5 and repeated every 28 days.

The dose administered will be determined using the body surface area (BSA) calculated at the beginning of each cycle. The BSA will be calculated from the height obtained at the baseline evaluation and from the weight obtained at the beginning of each cycle. The chart in Appendix B may be used to determine the dose of TMZ based on known BSA. A maximum BSA of 2.5 for TMZ dose calculation will be used for subjects with BSA>2.5.

TMZ dosing will be as follows, shown schematically in Table 6.2:

Cycle 1 Only:

[figure not shown]
The dose for the first cycle of TMZ is 150 mg/m²/day. Blood counts will be monitored day 15 and 22 for cycle 1.

Cycle 2 and higher:

The dose for cycle 2 and higher will be determined as follows:

- If during the first cycle, all clinically significant CTCAE non-hematological toxicity attributable to TMZ observed was Grade ≤ 2 (except for alopecia) and with platelets $\geq 100,000/\text{ul}$ and ANC $\geq 1500/\text{ul}$ then TMZ dose should be escalated to 200 mg/m²/day and this dose should be used as the starting dose for subsequent cycles.
- If treatment after cycle 1 has to be delayed because of ongoing clinically significant non-hematological toxicity of CTCAE grade > 2 , then no escalation is possible. If subject does not meet the criteria for dose escalation then the subject should remain at the 150mg/m²/day dose.
- If during the first cycle the subject experiences platelets $< 50,000/\text{ul}$ and/or ANC $< 1000/\text{ul}$ and/or a clinically significant non-hematologic toxicity $>$ grade 3 then subject should postpone therapy until ANC $> 1500/\text{ul}$ and platelets $>100,000/\text{ul}$ and reduce dose to 100mg/m²/day per dose reduction in Section 7.
- If the dose was not escalated at cycle 2 then the dose should not be escalated in further cycles.

Table 6.2 TMZ Dosing Modification For Cycle 2

The start of the each cycle will be scheduled 28 days \pm 3 days after the last day of the previous cycle.

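### After a cycle 1 Grade 3 non-hematologic toxicity, Section 6.2.2 and Table 7.2.1 give different cycle 2 temozolomide doses: 200 or 150 versus 100 mg/m²/day if attributed to ABT-888 (unsettled), and 150 versus 100 if attributable to temozolomide (text points to the table)

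*Combined protocol and SAP*

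**What the plan says.** Cycle 1 TMZ is 150 mg/m²/day. Section 6.2.2 then sets the cycle 2 dose in a short list of bullets.

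- **Bullet 1 (escalate).** If "all clinically significant CTCAE non-hematological toxicity attributable to TMZ observed was Grade" 2 or lower, with platelets at least 100,000 and ANC at least 1500, "then TMZ dose should be escalated to 200" mg/m²/day, and that becomes the starting dose for later cycles.
- **Bullet 2 (hold).** "If treatment after cycle 1 has to be delayed because of ongoing clinically significant non-hematological toxicity of CTCAE grade" above 2, escalation is barred. It adds: "If subject does not meet the criteria for dose escalation then the subject should remain at the" 150 dose.
- **Bullet 3 (reduce).** The dose falls to 100 for platelets below 50,000, ANC below 1000, or a "clinically significant non-hematologic toxicity $>$ grade 3 then subject should postpone therapy". It describes this as the Section 7 reduction.

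Section 7.2 gives its own rules in Table 7.2.1. For non-hematologic toxicity attributable to TMZ, the trigger is Grade 3 or higher. Nausea or vomiting counts only if it persists despite optimal antiemetics, and toxicities not named in the table count only if judged clinically significant. The action is one TMZ dose level down. The last row, headed "Attributable to ABT-888", is triggered by "Any Grade 3 or 4 toxicity which is not attributable to TMZ or underlying disease". It cuts ABT-888 to 20 mg every 12 hours and also says "Reduce TMZ dose by 1 dose level for the next cycle". Table 7.2.2 defines the levels as 200, 150, 100 and 75 mg/m²/day.

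**The concern.** The two sections divide Grade 3 events differently. Section 6.2.2 looks only at TMZ-attributable toxicity when deciding whether to escalate, and it reduces only above Grade 3. Table 7.2.1 reduces TMZ from Grade 3 upward, and it does so for ABT-888-attributed events as well. A physician working from Section 6.2.2 and one working from Table 7.2.1 could therefore give the same patient different TMZ doses in the cycle after a severe toxicity. In one case a written instruction is to escalate a myelosuppressive drug.

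The difference would last. Bullet 1 makes 200 the starting dose for later cycles, while Section 7.2 bars re-escalation after a reduction. There is little reassurance from experience at the current ABT-888 dose: Section 3.3 says the hematologic toxicity of starting at 30 mg twice daily is not clear from the primary study. What is at stake is patient safety and uniform dosing.

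**Working it through.** No error-rate formula applies. The check runs both sets of rules on the same patient.

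**Inputs.** Cycle 1 TMZ = 150, which is level 2 (Section 6.2.2, Table 7.2.2). One level down from level 2 is level 3 = 100.

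**Anchor.** Section 6.2.2, bullet 3, states 100 as the Section 7 reduction after cycle 1. Table 7.2.2 gives 150 → 100. The two agree, so one level is counted from the 150 actually given, not from a planned 200.

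**Case (i): Grade 3 event attributed to ABT-888, not to TMZ or underlying disease.** TMZ-attributable toxicity is Grade 2 or lower, ANC at least 1500, platelets at least 100,000.
- Section 6.2.2, cycle 2 not delayed for ongoing toxicity above Grade 2: bullet 1 is met, so 200.
- Section 6.2.2, cycle 2 delayed for that reason: bullet 2, so 150.
- Table 7.2.1, last row: 100 either way. The row is triggered by the event itself, so timely recovery does not remove the reduction.

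**Case (ii): clinically significant Grade 3 event attributable to TMZ** (nausea or vomiting: despite optimal antiemetics). ANC at least 1000, platelets at least 50,000.
- Section 6.2.2: bullet 1 fails (it needs Grade 2 or lower), bullet 3 fails (it needs more than Grade 3), so bullet 2 leaves 150.
- Table 7.2.1: the trigger of Grade 3 or higher is met, so 100.

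| Cycle 1 event | Section 6.2.2 | Table 7.2.1 | Per 5-day cycle (mg/m²) | Ratio |
|---|---|---|---|---|
| (i) no such delay | 200 | 100 | 200×5 = 1000 vs 100×5 = 500 | 2.0 |
| (i) delayed | 150 | 100 | 150×5 = 750 vs 500 | 1.5 |
| (ii) | 150 | 100 | 750 vs 500 | 1.5 |

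At an assumed body surface area of 1.8 m², Appendix B gives 360, 270 and 180 mg/day for 200, 150 and 100 mg/m².

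**Grade 4.** Table 7.2.1 gives 100. Section 6.2.2 gives 100 through bullet 3, but only if bullet 3 overrides the others. Read literally, bullet 1 still escalates to 200 after an ABT-888-attributed Grade 4 event with adequate counts, and the second sentence of bullet 2 still holds 150 after a TMZ-attributable one. Section 6.2.2 states no order among its bullets.

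**How many patients.** The documents give no rate. Section 3.3 indicates that the 41 primary-study patients were already enrolled and had cycle 1 at 40 mg ABT-888, so the current text mainly governs the expansion cohort of 20, with up to 22 allowed. As an assumption only, take the phase 1 serious adverse event counts in Section 7.1.1 as a range for qualifying Grade 3 events under either attribution: hematemesis 1/24 = 4.2%, vomiting 3/24 = 12.5%. Then 20 × 1/24 = 0.8 and 22 × 3/24 = 2.75, so about 1 to 3 patients. Serious events are not the same as Grade 3 events, the source was a dose-ranging study, and the range says nothing about how often case (i) alone would arise.

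**The case against.** The strongest reply is that Section 6.2.2 handles escalation and Section 7 handles reduction. Section 7.2 expressly sends Grade 3/4 toxicity attributable to TMZ to Table 7.2.1, and it bases the next dose on the worst non-hematologic toxicity of the previous cycle. Bullet 3 cites Section 7, and Section 6.2.2 closes its dosing text by referring there. For case (ii) this largely stands: the table has the better claim, and the threshold in bullet 3 is probably a slip for Grade 3 or higher. A reader might infer that both cases are equally open; the documents do not support that.

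For case (i) the reply falls short. The express direction to the table covers only TMZ-attributable toxicity. Section 6 says the cycle 2 increase follows Section 6.2.2, whose bullet 1 gives an explicit dose, and the general pointers to Section 7 state no precedence.

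A second reply is that case (i) is nearly empty, since Section 6.2.1 reports no known clinically significant toxicity of ABT-888 alone that calls for dose modification. That supports calling it rare. The protocol nonetheless wrote a table row for it.

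A third is that safeguards limit harm: case (i) requires adequate counts, Grade 3/4 treatment-related toxicity must resolve before redosing, and 200 is the planned cycle 2 dose. This is fair and tempers the safety concern, but it does not tell the physician which dose to give.

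**Conclusion.** The inconsistency is real in the text available and worth fixing. In case (i) the dose is 200 or 150 by Section 6.2.2 against 100 by Table 7.2.1, and nothing decides between them. In case (ii) it is 150 by the letter of Section 6.2.2 against 100, with the wider text favouring the table.

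Three stronger readings should be resisted. Grade 4 is not a clean agreement between the sections, because the 100 in Section 6.2.2 depends on an order of precedence it does not state. The two-fold difference should not be presented as common: it belongs only to case (i) without a delay. And the inconsistency does not reach the trial's inference: alpha, power and the objective response decision rule are unaffected.

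The conclusion assumes that one dose level is counted from the 150 given in cycle 1, which fits bullet 3. The Table 6.2 schematic of these same rules was not available; it could settle the matter, and its absence is not counted against the protocol.

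**What to change.** Amend Section 6.2.2 as follows.

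- (a) Add: *Where this section and Table 7.2.1 differ, Table 7.2.1 governs; a reduction rule takes precedence over the escalate and remain-at-150 rules.* This settles both Grade 3 cases and the Grade 4 ordering.
- (b) In bullet 1, allow escalation only if cycle 1 had no clinically significant non-hematologic toxicity of Grade 3 or higher attributable to TMZ or ABT-888.
- (c) In bullet 3, replace the threshold above Grade 3 with *a non-hematologic toxicity that requires TMZ reduction under Table 7.2.1*. Pointing to the table keeps its antiemetic condition; simply writing Grade 3 or higher would drop it and create a new mismatch.
- (d) Make the Table 6.2 schematic match.

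If the clinical team does not want TMZ reduced for ABT-888-attributed events, change the TMZ action in the last row of Table 7.2.1 to *maintain current TMZ dose* and still bar escalation in bullet 1.

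The cost is one added sentence, two wording edits and a check of one schematic, in a single amendment. Sample size, timelines and analysis do not change.

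### Section 7.2 gives conflicting attribution rules for dose reduction, so the same unrelated cytopenia or intercurrent illness can draw opposite instructions

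*Combined protocol and SAP*

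**What the plan says.** Several statements decide whether an event leads to a dose reduction. All but one are in Section 7.2.

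- **Opening text of 7.2.** It covers "Study drug interruptions for events that are clearly not related to the study drug, e.g., underlying cancer, planned surgical procedures or acute viral illnesses", and says these "should not necessitate a dose reduction and treatment may be delayed as necessary beyond 3 weeks".
- **TMZ text of 7.2.** "For any Grade 3/4 toxicities attributable to TMZ, dose reduction and/or delay guidelines should be followed per Table 7.2.1".
- **Table 7.2.1, haematologic row.** The label is "Hematologic Toxicity attributable to TMZ". For ANC below 1000/µL and/or platelets below 50,000/µL the action, after a hold until recovery, is "Reduce TMZ dose by 1 dose level at the next cycle". The count thresholds are starred to the footnote "Regardless of attribution".
- **Section 6.2.2, cycle 2 dosing.** Counts below the same two thresholds in cycle 1 lead to a TMZ reduction to 100 mg/m²/day. No attribution condition is stated.
- **ABT-888 bullet of 7.2, first event.** The reduction to 20 mg every 12 hours applies "For any subject who experiences Grade 3/4 toxicity which is not attributable to TMZ or the underlying disease".
- **Same bullet, second event.** Discontinuation starts from the same definition but adds a judgement that ABT-888 was the cause: "If a subject experiences a second Grade 3/4 toxicity which is not attributable to TMZ or the underlying disease and is thought", followed by the relation to ABT-888.
- **Table 7.2.1, ABT-888 row.** The event text repeats the definition by exclusion, but the row label confines it to events attributable to ABT-888. The action lowers ABT-888 to 20 mg and also lowers TMZ one level.

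Three further rules in 7.2 fix the consequences. A dose reduced for toxicity is not re-escalated. ABT-888 may be reduced only once. A patient at 75 mg/m²/day of TMZ who needs a further reduction because of toxicity stops both drugs.

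**The concern.** A dose-modification section should give one answer for one event. Here two kinds of event, both named in the opening text of 7.2 as examples of what is clearly unrelated to study drug, also fall under a reduction rule elsewhere in the section. No sentence sets precedence.

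What is at stake is consistent delivered dose and the meaning of the tolerability data. Safety and tolerability are a secondary objective (Section 2.3). Section 3.3 says that haematological toxicity in patients starting ABT-888 at 30 mg twice daily is not clear from the primary study, and that the BRCA1/2 expansion cohort is to characterise activity and safety further. If two investigators handle the same event differently, the number of reductions partly reflects which sentence was followed.

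**Working it through.** There is no plan figure to reproduce and no probability to compute. The check is to take one event at a time and read off what each statement instructs.

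**Case (a): ANC <1000/µL or platelets <50,000/µL, clearly due to the underlying cancer**

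| Statement | TMZ at next cycle |
|---|---|
| 7.2 opening text on unrelated events | no reduction called for |
| 7.2 TMZ text (table applies to TMZ-attributable toxicity) | table not triggered |
| Table 7.2.1 row label | row not triggered |
| Table 7.2.1 footnote on the thresholds | one level lower |
| 6.2.2, if the event is in cycle 1 | 100 mg/m²/day |

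The label and the footnote contradict each other within a single row. The footnote agrees with 6.2.2; the label agrees with the two text statements. Counting statements therefore does not settle the matter.

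**Case (b): a first Grade 3 acute viral illness**

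| Statement | ABT-888 | TMZ |
|---|---|---|
| 7.2 opening text | no reduction called for | no reduction called for |
| 7.2 ABT-888 bullet, first event, read literally | 20 mg every 12 hours | not mentioned |
| Table 7.2.1 event text and action, read literally | 20 mg every 12 hours | one level lower |
| Table 7.2.1 row label | row not triggered | row not triggered |

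The exclusion removes TMZ and the underlying disease, but not intercurrent illness. A viral illness is attributable to neither, so it stays inside the literal trigger. Three outcomes are possible: neither drug, ABT-888 alone, or both drugs reduced. The difference between the last two (bullet against table) remains even for an event that everyone attributes to ABT-888.

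**Size of one step** (TMZ levels from Table 7.2.2; ABT-888 doses from Sections 6.2.1 and 7.2)

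- TMZ 200 to 150: (200 − 150)/200 = 25%
- TMZ 150 to 100: (150 − 100)/150 = 33%
- TMZ 100 to 75: (100 − 75)/100 = 25%
- ABT-888 30 to 20 mg: (30 − 20)/30 = 33%

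At 75 mg/m²/day there is no lower level, so a further reduction counted as due to toxicity means stopping both drugs.

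**The case against.** The best defence of case (a) is that the footnote is a deliberate exception for blood counts. Both drugs are expected to contribute to myelosuppression, attribution of a low count is hard, 7.2 bases reductions on the lowest counts, and 6.2.2 also acts on counts alone. Patients enter with ANC of at least 1,500/mm³ and platelets of at least 100,000/mm³, so a severe cytopenia clearly unrelated to this combination may be uncommon. This is a coherent reading, but no text states it, and it leaves the row label and the TMZ text saying the opposite.

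For case (b), the row label points away from reduction, the opening text is a specific exemption that could be taken to qualify a general trigger, and toxicity might be read as drug-related by definition. The label does narrow the problem. The definitional argument is weak: 7.2 adds the qualifier of treatment-relatedness where it wants it, and excluding toxicity due to the underlying disease would be redundant if toxicity always meant drug-related. Section 7 also describes its rules as recommendations and guidelines, so a reduction can follow from the text but does not always have to.

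Three stronger readings are tempting and are not supported.

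- **A conflict over maximum delay.** The 3-week limit is tied to unresolved treatment-related toxicity and the longer delay to clearly unrelated events. These are two rules for two situations.
- **A frequent problem.** Section 3.3 reports 12 patients with grade 3/4 thrombocytopenia and 10 with grade 3/4 neutropenia among the first 41. These are described as expected toxicities, none is said to be unrelated, and all patients received ABT-888 at 40 mg twice daily in cycle 1. The counts do not measure how often the rules would collide.
- **An error in having different tests for the first and second ABT-888 events.** A stricter condition for discontinuation than for a first reduction may be intended.

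**Conclusion.** The contradiction stands as a defect of wording that changes what a site would do. In case (a) the same cytopenia leaves TMZ unchanged or lowers it one level (25% or 33%). At the lowest level, if the reduction is treated as due to toxicity, it takes the patient off both drugs. Case (b) is narrower because the row label points the other way, but the literal trigger still captures an event that the opening text exempts. Bullet and table also disagree on whether TMZ is lowered as well.

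This rests on two assumptions: the event is clearly unrelated to study drug, and a reduction made under the table is treated as made for toxicity, since the bar on re-escalation is worded that way. The documents do not give the frequency of such events. A reader might infer an effect on the response rate or on the trial's conclusion; the documents do not show one. The thresholds in Section 15.1 (5 of 41 and 7 of 20) and their error rates do not depend on these rules, and Section 15.4.2 does not exclude patients from the response analysis for an incorrect treatment schedule.

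**What to change.** Two reconciliations are needed.

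1. **Count-triggered reductions.** Bring the unrelated-event sentence and the TMZ text of 7.2, the haematologic row label and footnote of Table 7.2.1, and the cycle 1 rule of 6.2.2 into agreement, so that one stated attribution rule governs.
2. **ABT-888 reductions.** Bring the first-event bullet, the Table 7.2.1 row label and event text, and the unrelated-event sentence into agreement. State whether TMZ is also reduced.

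Which rule applies is for the investigators to decide. The cost is an amendment to wording in 6.2.2, 7.2 and Table 7.2.1. Sample size, endpoints and analysis are untouched. Attribution is already graded under 12.2.3.3, although for the study treatment as a whole and not for each drug. Recording the attribution and the table row applied at each dose change would let the safety report separate drug-related reductions from others.
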